EIT/EIS Systems: The EIT and EIS data collection will use custom systems owned by the Thayer School of Engineering at Dartmouth and housed in the Williamson Building at DHMC. The EIT/EIS data collection will be conducted only on stroke patients and healthy control subjects in this study. Electrical impedance systems are well established as patient safe and are commonly used in bioelectrical body impedance analysis [a], lung monitoring [b], breast cancer research [c], stroke research [d] and other research. **EIT system.** The EIT system (Fig. 1A) is a broadband (100 Hz–10 MHz) 20-channel data acquisition (DAQ) system with a SNR > 90 dB which possesses high speed capabilities (up to 80 frames/ second) [e]. The system is flexible and has a modular hardware and software design that allows for performance upgrades such as DAQ frame rate and SNR. It uses National Instruments (NI) hardware and software modules, which offer inherent compatibility over generations of hardware and software revisions. Digital switches allow data to be recorded from up to 120 electrodes. **EIS system.** The EIS system operates similarly to the EIT system. However, it will only use up to 30 channels. The custom-designed system allows for switching between channels and applies currents over a bandwidth of 100 Hz-500 kHz. Prior versions of both the EIT and EIS systems have been safely implemented in other IRB-approved human subjects studies here at DHMC [f]. The EIT and EIS systems comply with International Electrotechnical Commission (IEC) requirements for safety and essential performance of medical electrical equipment (IEC 60601-1). The EIT system has been reviewed and approved by DHMC Biomedical Engineering. The EIS system is the next iteration of this and will be approved by DHMC Biomedical Engineering prior to any patient use.

Optical Scanners:

The optical scanners are used to recover precise locations of electrodes and landmarks, e.g. nasion (bridge of nose), left and right pre-auricular points, for registration with the MR imaging data. The scanners will either be a Geodesics Photogrammetry System 3 (GPS3)

(<https://www.philips.com.tw/healthcare/product/HC4601902/geodesic-photogrammetry-system-3-research->

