EEG data will be exported and pre-processed by Matlab programs developed in-house. The global field potential (GFP) and entropy across all 256 or 128 channels will be computed at each time point. GFP is sensitive to polarity changes across channels, while entropy could be helpful to eliminate EMG artifacts. Interictal epileptiform discharges (IEDs) will be identified by auto-thresholding both GFP and entropy. The source localization of IEDs will be determined using inverse solutions in Brainstorm. If applicable, intracranial EEG and/or intraoperative ECoG recordings will be used to evaluate the accuracy of IED source localizations. In addition to the self-developed detection algorithm, we will also utilize Spike Beacon software, which is developed by EGI to detect interictal discharges and compare it with our own algorithms.

For each subject, the EEG signals will be analyzed in 84 regions of interest (ROIs) defined according to the 42 Brodmann areas (BAs) for the left and right hemispheres. These ROIs will be defined for each subject using FreeSurfer. Low resolution electromagnetic tomographic analysis (LORETA) will be used to inversely estimate the EEG signal from these ROIs to localize cortical and subcortical sources from EEG signal generators. The EEG data will be investigated in the following aspects: 1) frequency content, including relative composition of delta (0.5-3 Hz), theta (3-7 Hz), alpha (7-13 Hz), beta (13-30 Hz), and gamma (>30 Hz) EEG oscillations along with their percent ratios; and 2) spatial heterogeneity, including global functional connectivity and interhemispheric asymmetry in the above-mentioned frequency bands.

For patients with peripheral nerve dysfunction, we will compare the amplitude and latency of the SSEP responses, and the source localization on individual brains between pre- and post-operative visits.

Stroke hdEEG-, EIT-, and EIS-based analysis

The aim of the hdEEG, EIT, and EIS analyses is to investigate how well these technologies function alone or in combination with each other or with other information, such as the NIHSS, CT or MRI-images to aid in 1) discriminating hemorrhagic from ischemic stroke, 2) monitoring of stroke patients, and 3) predicting stroke outcomes.

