hdEEG. The stroke hdEEG-processing will follow the steps as outlined above. In particular to stroke, we will additionally 1) perform spectral analysis to identify regions with EEG slowing (i.e., stroke region(s)), 2) use SSEP to assess sensorimotor function, and 3) investigate a novel algorithm, called EEG-No Source Imaging (NSI), which aims to localize the stroke through a hypothesis testing approach.

EIT. The collected EIT data will be used to construct 3D images of electrical properties within the head using single- and multi-frequency image reconstruction approaches. The reconstructions rely on a 3D tetrahedral mesh of the domain; nominal and patient-specific meshes will be considered. We will utilize the FreeSurfer-segmented data for this effort. We will consider reconstructions with and without structural information, e.g. skull, CSF, and stroke boundaries. Algorithms will also be considered that incorporate both EEG and EIT information. Electrical properties of the stroke, penumbra, and other ROIs will be considered for analysis.

EIS. The EIS data will look at raw impedance magnitudes and spectral properties of the acquired multi-frequency traces. Phase, magnitude, resistance, reactance and spectral fitting metrics will all be extracted

from the signals and explored in the development of a novel algorithm to isolate an intracranial abnormality, e.g., stroke region(s). This processing will include analysis of the heterogeneity of the surface potentials and will be compared to prior patient imaging to test the ability to detect, identify and localize stroke. Data will be explored in three cohorts: 1) all stroke vs all healthy 2) all ischemic vs all hemorrhagic and 3) large vs small infarct. Potential augmentation of EIS signals with EIT or EEG traces will be explored as well.

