Statistical Analyses. Metrics from EEG, EIT, and EIS analyses will be used for structural and functional assessment. **Structural:** We will use Receiver-Operator Characteristic (ROC) curve analysis to produce clinical metrics (area under the curve, true and false positive rates, true and false negative rates, sensitivity, specificity, positive predictive value, negative predictive value, accuracy, etc.) for the detection testing (discriminating stroke type). Accuracy (position errors) will be used to assess stroke localization. Linear regression will be used to correlate metrics/electrical properties with volume and R^2 and p-values will define the goodness of fit. **Functional:** We will explicitly evaluate linear and multi-parameter regression models as part of our analysis (including correlation, p-values, and standard deviations of residuals). Comparisons will be made between hdEEG, EIT, and EIS techniques and SSEP metrics to determine which provides the most information or if they provide complementary information through multiple linear regression and/or analysis of variance (ANOVA).

5. Study Progress Monitoring

Note: appropriate monitoring may include periodic assessment of the following:

- data quality
- timelines
- recruitment and enrollment

Provide a description of the methods which will be used to determine the progress of the study, including periodic assessments of data quality, timelines, recruitment, and enrollment as appropriate:

The PI and co-investigators will periodically review progress of the experimental testing, including assessments of data quality, patient recruitment, and progress toward validation of test effectiveness. Adverse reactions or problems with the testing performed at DHMC or reported by others will be addressed immediately and reported to the Dartmouth-Hitchcock Health Institutional Review Board (D-HH IRB).

6. Risks & Benefits

Note: Risks may be physical, psychological, social, legal, economic, to reputation, or others.

a. Describe any potential risks, their likelihood and seriousness:

This study will not create additional risk to patients with neurological disorders due to the hdEEG recording, and may result in only minimal risk associated with electrical impedance measurements.

hdEEG

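### Stroke-type ROC figures (25 vs 25 patients) have no fixed metric, direction, model or cut-point and no internal validation, so they are likely to be optimistic

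*Combined protocol and SAP*

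**What the plan says.** All references are to the combined protocol and SAP.

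- **Section 4, Stroke hdEEG-, EIT-, and EIS-based analysis.** The aim is to learn "how well these technologies function alone or in combination with each other or with other information". Discriminating hemorrhagic from ischemic stroke is the first of three listed uses.
- **Section 4, EIS.** "Phase, magnitude, resistance, reactance and spectral fitting metrics will all be extracted", and these are to be "explored in the development of a novel algorithm to isolate an intracranial abnormality". One of three contrasts to be explored is "all ischemic vs all hemorrhagic". The paragraph adds: "Potential augmentation of EIS signals with EIT or EEG traces will be explored as well".
- **Section 3, EIT/EIS Systems.** The EIS device "applies currents over a bandwidth of 100 Hz-500 kHz", so each metric type can be read at many frequencies.
- **Section 4, Statistical Analyses (Structural).** "We will use Receiver-Operator Characteristic (ROC) curve analysis to produce clinical metrics" for discriminating stroke type. The inputs are described only as metrics from the three modalities.
- **Section 10.b.** 25 ischemic and 25 hemorrhagic patients are planned, in what is called a pilot. Conductivity at 1 kHz appears there for sample size only and is not named as the ROC metric.
- **Section 5.** The investigators will review "progress toward validation of test effectiveness". This is progress monitoring, and no validation method is given.

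The documents do not mention cross-validation, bootstrap, a training and test split, or a second cohort.

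**The concern.** An ROC curve gives an honest estimate when the score and its direction were fixed before the data were seen. If the analyst looks at several metrics in 50 patients and reports the best one, its AUC includes the luck that made it best. If the cut-point is also picked on those patients, sensitivity, specificity and accuracy gain a further upward bias, which is present even for one pre-specified metric. Fitting a combination has the same effect, because each added metric tends to raise the apparent AUC whether or not it helps.

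In a pilot, the practical harm is carrying the wrong metric, or an overstated accuracy, into the design of the next study.

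**Working it through.** **1. Planning figure and signal sizes.** The documents give no ROC figure. The only design calculation for this contrast is in section 10.b: 0.11 vs 0.075 S/m, SD 0.025, ten per group, 95% power.
- d = (0.11 − 0.075)/0.025 = 1.4.
- At an assumed alpha of 0.05, ten per group gives 93.1% power (one-sided, normal approximation) or 84.1% (two-sided t-test). The 95% is therefore roughly reproduced only one-sided. That is a separate matter; here the calculation serves only to supply d.
- Section 10.b reports about a 50% loss of signal in vivo. With the SD unchanged (assumed), d = 0.7 and the true AUC is Φ(0.7/√2) = 0.690.
- Its doubling of the sample size implies instead d = 1.4/√2 = 0.99, with AUC Φ(0.99/√2) = 0.758.

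**2. Chance variation of one fixed metric, 25 vs 25, no signal.** SD of AUC = √(51/(12 × 625)) = 0.082, with mean 0.50. There is no bias.

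**3. Best of K metrics.** Simulation with 25 + 25 patients, normal metrics, equal pairwise correlation rho, direction chosen on the data, and signal (if any) in one metric only. K and rho are assumptions. K = 5 matches the five metric types named under EIS, and K = 20 allows for several frequencies or modalities.

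| True signal | K | rho | Apparent AUC | AUC in new patients |
|---|---|---|---|---|
| none | 5 | 0.5 / 0.8 / 0.95 | 0.62 / 0.61 / 0.59 | 0.50 |
| none | 20 | 0.5 / 0.8 / 0.95 | 0.66 / 0.63 / 0.60 | 0.50 |
| d = 0.7 | 20 | 0.5 / 0.8 | 0.71 / 0.71 | 0.63 / 0.65 |
| d = 0.99 | 20 | 0.5 / 0.8 | 0.76 / 0.76 | 0.73 / 0.74 |

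For K = 5 the excess is about 0.04 at d = 0.7 and about 0.02 at d = 0.99. With no signal and K = 20, an apparent AUC of at least 0.70 occurs in about 16% of studies at rho 0.5, 9% at rho 0.8 and 4% at rho 0.95.

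**4. Cut-point chosen on the data (Youden), one fixed metric.**
- No signal: mean apparent sensitivity 0.650 and specificity 0.508, so balanced accuracy = (0.650 + 0.508)/2 = 0.579 instead of 0.50.
- d = 0.7: the AUC is unbiased (0.691 vs 0.690), but sensitivity shows 0.72 against a true 0.66, and specificity 0.66 against 0.59.

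**5. Combinations, if their ROC values are reported.** One metric with d = 0.7 plus two null metrics in a linear discriminant (assumed model):
- rho 0: apparent 0.718, new patients 0.658. The combination looks better than the single metric (0.690) but is worse.
- rho 0.5: apparent 0.754, new patients 0.700. It is slightly better than the single metric, by far less than it appears.

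Apparent AUC cannot tell these two cases apart.

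**6. Does internal validation repair it?** All choices were repeated inside folds or resamples.
- Ten-times-repeated 5-fold cross-validation: null AUC 0.494 to 0.500 (SD about 0.09 to 0.12). At d = 0.7 it lies 0.00 to 0.02 below new-patient AUC.
- Bootstrap optimism correction: about 0.55 instead of 0.50 under the null for best of 20, but less variable. Root mean square error against new-patient AUC, bootstrap vs cross-validation, best of 20: 0.078 vs 0.099 (null), 0.095 vs 0.118 (d = 0.7, rho 0.5) and 0.094 vs 0.102 (d = 0.99, rho 0.5).

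**7. Predictive values.** With sensitivity = specificity = 0.70 and hemorrhagic share p, PPV for hemorrhage = 0.7p/(0.7p + 0.3(1 − p)). This gives 0.70 at p = 0.5, 0.50 at p = 0.3 and 0.37 at p = 0.2. The last two shares are assumptions; the documents give none.

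**The case against.** **This is a pilot, and exploration is its purpose.** That is right, and exploring is not the fault. But the Statistical Analyses paragraph promises clinical accuracy figures with no exploratory label and no correction.

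**The bias may be small.** This largely stands if the signal is strong. At d = 0.99 the excess is 0.02 to 0.04, against a sampling SD of the AUC of about 0.06. Magnitude with phase, and resistance with reactance, are two forms of the same complex impedance, and neighbouring frequencies may be highly correlated, so the effective number of candidates may be low. The direction of the bias is secure; its size is not.

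**Stronger readings that the documents do not support.**
- A reader might infer that the new EIS algorithm is a stroke-type classifier trained and tested on the same patients. It is described as isolating a stroke region, and localization is to be judged by position error. The point therefore rests on the choice of metric, combination and cut-point.
- A reader might take same-patient selection and scoring as stated. It is inferred, because no other patients are described.
- A reader might multiply the 84 EEG regions by five bands to get 420 candidates, or fit a discriminant to twenty noise metrics. Both give larger figures, but the plan commits to neither.
- A reader might infer a planned ranking of modalities by AUC. None is stated. The modality comparison in the Functional part uses regression or ANOVA and is outside this point, as is stroke vs healthy.

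**Conclusion.** The concern holds in this form: stroke-type ROC figures from 25 vs 25 patients would be drawn from several explored metrics and combinations, with nothing fixed in advance and no internal validation. Choosing the metric or model on the scored patients inflates AUC. Choosing the cut-point inflates sensitivity and specificity, even for one fixed metric (balanced accuracy 0.58 instead of 0.50 with no signal).

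For 5 to 20 metrics at rho 0.5 to 0.95, mean apparent AUC with no signal is about 0.59 to 0.66. The excess over new-patient AUC is about 0.04 to 0.08 at d = 0.7 and 0.02 to 0.04 at d = 0.99. These sizes rest on the assumed K, rho, normal metrics and a single informative metric, and on the inference that no other patients will be used. The plan should be changed before analysis; the gap does not undermine the study itself.

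**What to change.** Add to Statistical Analyses (Structural) in section 4:

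> For stroke type, ROC AUC, sensitivity, specificity, predictive values and accuracy will be reported with internal validation by participant (repeated stratified 5-fold cross-validation, or a bootstrap optimism correction) in which all metric, frequency, electrode/ROI, direction, model and cut-point choices are repeated within each training fold or resample. Under cross-validation, AUC will be averaged over test folds, and threshold-based figures will be computed from the pooled held-out classifications. Uncorrected values will be labelled apparent and exploratory. Any ROC comparison of single and combined modalities will use validated values in the same patients, namely those with all compared modalities. Predictive values reflect the roughly 50:50 design mix.

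The same-patients clause is needed because section 3 lets a session collect EIT, EIS or both, so the modality subsets may differ.

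Optionally, pre-specify one primary metric and its direction. Its AUC then needs no correction, but its cut-point still does unless that is fixed too.

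Either validation method is defensible, and the choice should be stated in advance. Cross-validation is nearly unbiased but noisier; bootstrap correction varies less but leaves some optimism when there is no signal. The cost is a little analysis code and lower, less precise headline figures. No new data or patients are needed.

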After completing pilot studies, we will focus on those tests which appear to be eliciting consistent, localized brain activation. Under these circumstances adequate statistical power should be obtained by repeating these tests in 15-20 patients. However, for the short-term epilepsy study we are more interested in investigating the correlation between the spike localizations and other clinical diagnostic results. Due to their very deep location, the determination of spike localization could be challenging in some epilepsy patients. In order to have a better understanding of the efficacy of using high-density EEG to provide useful information for various types of epilepsy patients (i.e., temporal vs. extra-temporal), we would like to perform this study on a larger patient size.

For the EIT/EIS cohort, sample size is based on previous contrasts observed in ex-vivo ischemic and hemorrhagic tissue [a]; specifically, the conductivities at 1 kHz were 0.075 Siemens/meter (S/m) for hemorrhagic tissue and 0.11 S/m for ischemic tissue. For a reported standard deviation of 0.025 S/m, there would be a 95% power to detect significant differences through an unpaired t-test with a group sample size of ten subjects for each cohort (20 total). An initial investigation into non-invasive in-vivo signals results in an ~50% drop in signal, requiring a 2x increase in sample size and a total desired cohort of n=50, split into two sub-cohorts of n=25 ischemic and hemorrhagic stroke, respectively. However, as this is a pilot study, these are projections; should initial data indicate higher signal contrast and lower standard deviations than anticipated, the numbers will be revisited to ensure optimized patient recruitment.

[a] Yang, L., Zhang, G., Song, J., Dai, M., Xu, C., Dong, X., & Fu, F. (2016). Ex-Vivo Characterization of Bioimpedance Spectroscopy of Normal, Ischemic and Hemorrhagic Rabbit Brain Tissue at Frequencies from 10 Hz to 1 MHz. *Sensors (Basel, Switzerland)*, 16(11).

c. Define the target population:

Epilepsy patients

Patients with a diagnosis of epilepsy will be considered for participation if they are interested and in the judgment of the research team they require further mapping or are capable of performing the functional and/or cognitive tasks required of the study.

Inclusion criteria:

1. Able to perform the tasks
2. Subject or legally authorized representative able to provide appropriate consent

Exclusion criteria:

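### The volume regression names no stroke-type term, although the plan expects electrical properties to differ by type; adding a type main effect is a cheap improvement

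*Combined protocol and SAP*

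**What the plan says.** Section 4, Statistical Analyses, gives the volume analysis one sentence under Structural: "Linear regression will be used to correlate metrics/electrical properties with volume", with R^2 and p-values as the measure of fit. It names no covariate, interaction or separate fit by stroke type. Under Structural, stroke type appears only as the target of the ROC analysis. Multi-parameter regression is mentioned under Functional, with no covariates listed. The EIS paragraph of Section 4 lists ischemic against hemorrhagic stroke and large against small infarct as separate comparisons; neither is tied to the volume regression.

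Section 10b expects the types to differ electrically: "the conductivities at 1 kHz were 0.075 Siemens/meter (S/m) for hemorrhagic tissue and 0.11 S/m for ischemic tissue". It adds "For a reported standard deviation of 0.025 S/m", then "An initial investigation into non-invasive in-vivo signals results in an ~50% drop in signal", and plans "two sub-cohorts of n=25 ischemic and hemorrhagic stroke, respectively". Section 3 (short-term hdEEG/EIS/EIT study) lists type of stroke among the clinical information collected for stroke patients.

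**The concern.** The regression asks whether a metric tracks lesion volume. The same metrics are expected to differ between hemorrhagic and ischemic stroke, and that expectation is the basis of the cohort size. If both types enter one regression without a type term, two things can happen.

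- Whatever the volumes are, the type difference goes into the residual. R^2 falls and power for volume is lost.
- If mean volume differs by type, part of the type difference is credited to volume. Depending on the direction, this creates an apparent volume effect or hides part of a real one.

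R^2 and the p-value are the two quantities the plan will use to judge the fit, and both are affected. Type is already recorded, so the information needed to avoid this is in hand.

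**Working it through.** **Inputs from Section 10b.** Conductivity 0.075 S/m (hemorrhagic) and 0.11 S/m (ischemic), SD 0.025 S/m, about 50% signal loss in vivo, 25 patients per type.

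**Assumptions, not in the documents.** Two-sided 5% level; 0.025 is the within-type SD and is unchanged by the signal loss; the volume gaps and true volume effects used below.

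**1. The plan's own figure.** Section 10b claims "95% power to detect significant differences through an unpaired t-test" with a "group sample size of ten subjects for each cohort (20 total"). The noncentrality is 0.035 / (0.025 × √(2/10)) = 3.13. Power is 87.9% (two-sided normal), 84.1% (two-sided t), 93.1% (one-sided normal) or 91.4% (one-sided t). Only the one-sided normal figure comes within 2 points of 95%. That is a separate matter; what is needed here is the effect size. The plan gives no figure for the volume regression.

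**2. Size of the type effect.** 0.035 / 0.025 = 1.4 SD ex vivo. Halved: 0.0175 / 0.025 = 0.7 SD.

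**3. Share of variance due to type.** With a 25:25 split, the between-type variance is (difference/2)².

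- 1.4 SD: 0.0175² / (0.025² + 0.0175²) = 0.329. Residual variance without the term is 1 + 0.7² = 1.49 times the within-type value.
- 0.7 SD: 0.00875² / (0.025² + 0.00875²) = 0.109. The factor is 1 + 0.35² = 1.12.

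**4. Power when volume does not differ by type.** There is no bias. For an assumed within-type correlation of 0.4 (simulated, 25 + 25), power for volume rises with the type term from about 78% to 83% at 0.7 SD, and from about 65% to 83% at 1.4 SD.

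**5. False positives when volume differs by type.** Let g be the ischemic-minus-hemorrhagic gap in mean volume, in within-type SDs, β the true slope and δ the type difference. Without a type term the slope tends to β + δ(g/4)/(1 + g²/4). At g = 1 and β = 0 this is 0.0175 × 0.25/1.25 = 0.0035 S/m per volume SD at 0.7 SD, and 0.035 × 0.25/1.25 = 0.0070 at 1.4 SD. Rejection rates for volume with no true volume effect (20,000 simulated trials per setting):

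| Assumed gap (SD) | No type term, 0.7 SD | No type term, 1.4 SD |
|---|---|---|
| 0 | 5.4% | 5.2% |
| 0.25 | 5.8% | 7.7% |
| 0.5 | 8.8% | 16.2% |
| 0.8 | 13.6% | 33.3% |
| 1.0 | 18.0% | 45.4% |

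With a type term the rate is 4.6% to 5.3% throughout.

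**6. Masking.** Assume a real slope of 0.0125 S/m per volume SD and larger hemorrhages. At 1.4 SD, gaps of 0.5 and 1.0 SD pull the mean fitted slope down to 0.0083 and 0.0053, and power to 49% and 28%. At 0.7 SD the slopes are 0.0104 and 0.0089, and power 78% and 73%. With the type term the slope is unbiased and power is about 91% in each case.

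**The case against.** **The plan does not say the types are pooled.** This stands. A reader might infer that the plan commits to one predictor fitted over all 50 stroke patients; the text does not say so. The EIS paragraph already separates the types, and its large-against-small comparison could be read as lying within ischemic stroke. A fit within each type would also answer the concern. But no such fit is written for the volume regression, so the supportable claim is that handling of type is unspecified and pooling is allowed.

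**The bias needs a volume gap for which the documents give no value.** This stands, which is why the range starts at zero, where the false-positive rate is nominal. The loss of precision in steps 3 and 4 needs no gap.

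**The type effect is ex-vivo tissue conductivity at 1 kHz.** This stands too. The regression also covers EEG, EIT and EIS metrics for which no type difference is given. For this cohort 0.7 SD is the more relevant case.

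**The unadjusted association may itself be of interest.** When type is not yet known, an unadjusted R^2 is a legitimate description. It can be kept, but it answers a different question from whether volume matters within a type.

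**A fuller model has a price.** At 0.7 SD and a common within-type correlation of 0.4, a joint test of volume and volume-by-type has about 73% power, below the 78% of the unadjusted model. Pooling slopes only if they agree would be an undefined pretest with little power. Both are good reasons to stop at a main effect.

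A reader might also infer that the two types have volume slopes of opposite sign that cancel when pooled. That requires a normal-tissue conductivity between the two lesion values, which the documents do not give, so it is not claimed.

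**Conclusion.** The point holds as a cheap improvement of minor severity. The volume regression is written without a type term or a by-type fit, while the plan's own figures put the type difference at 1.4 SD ex vivo and about 0.7 SD after signal loss.

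The loss of precision follows from the plan's inputs if the types are pooled and conductivity behaves as Section 10b assumes. False positives and masking depend further on an unknown difference in volume between types: the text shows that they can occur, not that they will. The upper figures, about 18% and 45%, belong to an assumed gap of 1 SD.

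Section 10b calls the study a pilot, and neither the sample size nor any decision rule rests on this regression.

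**What to change.** State in Section 4 that the volume regression includes stroke type as a main effect, and that the primary p-value for volume comes from the type-adjusted slope, reported with its confidence interval. Also report the slope and R^2 within each type, and give the volume-by-type interaction as descriptive only, with no rule that pools the slopes depending on whether they appear to agree. The unadjusted R^2 may stay as a secondary description.

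The cost is 1 degree of freedom and a little more output; no new data are needed. The within-type estimates rest on about 25 patients each and will be imprecise, which the report should say.
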